2.4 Endpoints

The primary endpoint is pathological complete response (pCR) as defined by no evidence of tumor cells in the final surgical specimen
The secondary endpoints are ORR per RECIST 1.1 criteria, recurrence disease-free and incidence of AEs

3.0 PATIENT ELIGIBILITY

CONFIDENTIAL

This material is the property of the [UC Irvine Chao Family Comprehensive Cancer Center](#). Do not disclose or use except as authorized in writing by the study sponsor.

Eligibility waivers are not permitted. Subjects must meet all of the inclusion and exclusion criteria to be registered to the study. Study treatment may not begin until a subject is registered.

3.1 Inclusion Criteria

- 3.1.1 Patients must have a diagnosis of HR+ breast cancer. To fulfill the requirement of HR+ disease, a breast cancer must express, by immunohistochemistry (IHC), at least one of the hormone receptors (ER, progesterone receptor [PgR]) as defined in the relevant American Society of Clinical Oncology (ASCO)/College of American Pathologists (CAP) Guidelines (Hammond et al. 2010):
 - For ER and PgR assays to be considered positive, $\geq 1\%$ of tumor cell nuclei must be immunoreactive by immunohistochemistry (IHC) (Hammond et al. 2010).
- 3.1.2 Patients must have Loco regional breast cancer (Stage I, Stage II and stage III per AJCC 8th edition criteria for staging of breast cancer)
- 3.1.3 Patients must have localized recurrence while on adjuvant endocrine therapy
- 3.1.4 Patients must have any known molecular evidence of endocrine resistance by next generation sequencing
- 3.1.5 Age ≥ 18 years.
- 3.1.6 ECOG performance status 0-1
- 3.1.7 Have post-menopausal status as defined by following:
 - Prior bilateral oophorectomy
 - Age ≥ 60 years
 - Age < 60 and amenorrheic (non-treatment-induced amenorrhea secondary to tamoxifen, toremifene, ovarian suppression, or chemotherapy) for at least 12 months. Follicle-stimulating hormone (FSH) and estradiol must be in the postmenopausal range.
- 3.1.8 Have at least one measurable disease as defined per RECIST 1.1
- 3.1.9 Adequate organ and marrow function as defined below:
 - Hemoglobin* > 8 g/dL
 - Absolute neutrophil count $\geq 1,500/\text{mcL}$
 - Platelets $\geq 100,000/\text{mcL}$
 - Total bilirubin $\leq 1.5 \times$ institutional ULN

Patients with Gilbert's syndrome with a total bilirubin ≤ 2.0 times ULN and direct bilirubin within normal limits are permitted

 - AST (SGOT)/ALT (SPGT) $\leq 2.5 \times$ institutional ULN
 - Creatinine $\leq 1.5 \times$ institutional ULN

**Patients may receive transfusion of packed red blood cells (PRBC) to achieve this hemoglobin level at the discretion of the investigator; however, initial study drug treatment must not begin earlier than the day after the PRBC transfusion.*

CONFIDENTIAL

This material is the property of the [UC Irvine Chao Family Comprehensive Cancer Center](#). Do not disclose or use except as authorized in writing by the study sponsor.

- 3.1.10 Able to swallow oral medications
- 3.1.11 Patients who received adjuvant radiotherapy must have completed and fully recovered from the acute effects of radiotherapy. A washout period of at least 14 days is required between end of radiotherapy and screening for the study.
- 3.1.12 Patients who received chemotherapy must have recovered (Common Terminology Criteria for Adverse Events [CTCAE] Grade ≤1) from the acute effects of chemotherapy except for residual alopecia or Grade 2 peripheral neuropathy prior to enrollment. A washout period of at least 21 days is required between last chemotherapy dose and enrollment (provided the patient did not receive radiotherapy).
- 3.1.13 Any known markers of response or resistance to CDK 4/6 inhibitors to be present in the biopsy specimen
- 3.1.14 If patients have been treated with prior Neo-Adjuvant chemotherapy at the time of primary diagnosis and not at the time of recurrence, they will be included in the study.
- 3.1.15 Must be able to sign a written informed consent, are reliable, willing to be available for the duration of the study and are willing to follow study procedures

3.2 Exclusion Criteria

- 3.2.1 Stage IV metastatic breast cancer
 - This study will utilize the American Joint Committee on Cancer (AJCC) staging system, eight edition that provides a strategy for grouping patients with respect to prognosis. The AJCC has designated staging by TNM classification. The researchers will also review tumor size, lymph node status, and estrogen-receptor and progesterone-receptor levels in the tumor tissue.
- 3.2.2 Patients with HER2 positive and triple negative breast cancer
 - To fulfill the requirement of HER2- and Triple negative disease, a breast cancer must not demonstrate, at initial diagnosis or upon subsequent biopsy, overexpression of HER2 or should not express ER or PR receptors by either IHC or in-situ hybridization (ISH) as defined in the relevant ASCO/CAP guidelines (Wolff et al. 2013).
- 3.2.3 Inflammatory breast cancer
- 3.2.4 Newly diagnosed endocrine naïve patients
- 3.2.5 No molecular evidence of endocrine resistance
- 3.2.6 Prior treatment with any CDK 4/6 inhibitor and/or Fulvestrant
- 3.2.7 Pre-menopausal women
- 3.2.8 Are currently receiving an investigational drug in a clinical trial or participating in any other type of medical research judged not to be scientifically or medically

CONFIDENTIAL

This material is the property of the [UC Irvine Chao Family Comprehensive Cancer Center](#). Do not disclose or use except as authorized in writing by the study sponsor.

compatible with this study. If a patient is currently enrolled in a clinical trial involving non-approved use of a device, then agreement with the principal investigator is required to establish eligibility

- 3.2.9 Have had major surgery within 14 days prior to enrollment to allow for post-operative healing of the surgical wound
- 3.2.10 Have initiated bisphosphonates or approved RANK ligand therapy for breast cancer with osseous metastasis, if patients are received Zolendronic acid or Denosumab in the adjuvant manner then such patients will be allowed participate
- 3.2.11 Have serious preexisting medical conditions that, in the judgment of the investigator, would preclude participation in this study (for example, history of major surgical resection involving the stomach or small bowel or preexisting Crohn's disease or ulcerative colitis, interstitial lung disease, severe dyspnea at rest, any pre-existing chronic condition resulting in baseline grade 2 or higher diarrhea)
- 3.2.12 Have a personal history of any of the following conditions: syncope or cardiovascular etiology, ventricular tachycardia, ventricular fibrillation or sudden cardiac arrest
- 3.2.13 Have a history of any other cancer (except for non-melanoma skin cancer or carcinoma in situ of the cervix) unless in complete remission with no therapy for a minimum of three years or have received an autologous or allogeneic stem-cell transplant
- 3.2.14 Have an active bacterial or fungal infection or a detectable viral infection (for example HIV or viral hepatitis). Screening is not required for enrollment
- 3.2.15 Recent therapy with a biologic agent or a monoclonal therapy is excluded. Wash out of at least three half-lives of monoclonal antibody would be required to be enrolled.

4.0 TREATMENT PLAN

4.1 Treatment Dosage and Administration

- 4.1.1 Abemaciclib will be administered orally at the dose of 150 mg twice daily. Fulvestrant will be administered intramuscularly at an initial loading dose of 500mg on days 1 and 15 of the first cycle and then 500 mg intramuscularly every first day of each subsequent cycle. One cycle is 28 days.

REGIMENT DESCRIPTION				
Agent	Dose	Route	Schedule	Cycle Length

CONFIDENTIAL

This material is the property of the [UC Irvine Chao Family Comprehensive Cancer Center](#). Do not disclose or use except as authorized in writing by the study sponsor.

Abemaciclib	150 mg	Oral (PO)	BID	4 weeks (28 days)
Fulvestrant	500 mg	IM	C1D1, C1D15, and D1 of each subsequent cycle	

4.1.2 Supportive Care Guidelines

Necessary supportive measures for optimal medical care will be given throughout the study including antidiarrheal, blood components etc. Additional care will be administered as indicated by the treating physician and the subject's medical need. All the concomitant medications and supportive therapy administered during the 30 days prior to the first dose until 30 days after the last dose must be recorded in OnCore eCRF.

4.2 **Toxicities and Dosing Delays/Dose Modifications**

Any patient who receives treatment on this protocol will be evaluable for toxicity. Each patient will be assessed for the development of toxicity according to the Time and Events table (Section 5.4). Toxicity will be assessed according to the NCI Common Toxicity Criteria for Adverse Events (CTCAE), version 5.0. Dose adjustments should be made according to the system showing the greatest degree of toxicity.

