4.2.1 Abemaciclib Dose Modification and Management

Please refer to the following tables for dose modifications for adverse reactions related to abemaciclib. If dose reduction is necessary, decrease the dose by 50 mg at a time. Discontinue abemaciclib for patients unable to tolerate 50 mg twice a day (BID).

Abemaciclib Dose Modifications for Adverse Events

Dose Level	Abemaciclib dose in combination with fulvestrant
Recommended Starting Dose	150 mg
First Dose Reduction	100 mg
Second Dose Reduction	50 mg
Third Dose Reduction	Not applicable

Hematologic Toxicities

Hematologic toxicities including neutropenia, leukopenia, anemia, and thrombocytopenia have been observed in patients treated with abemaciclib, and causality has been established. Severe (Grade 3 and 4) neutropenia was observed in patients receiving abemaciclib. Patients should be monitored closely for signs of infection, anemia, and bleeding.

Hematologic Toxicity Dose Management Guidelines
Monitor complete blood counts prior to the start of abemaciclib therapy, every 2

CONFIDENTIAL

This material is the property of the [UC Irvine Chao Family Comprehensive Cancer Center](#). Do not disclose or use except as authorized in writing by the study sponsor.

weeks for the first 2 months, monthly for the next 2 months, and as clinically indicated.

CTCAE Grade	Action
Grade 1-2	No dose modification required
Grade 3	Suspend dose until toxicity resolves to \leq Grade 2. Dose reduction is not required.
Grade 3, recurrent, or Grade 4	Suspend dose until toxicity resolves to \leq Grade 2. Resume at next lower dose.

If blood cell growth factors are required, suspend abemaciclib dose for at least 48 hours after the last dose of blood cell growth factor and until toxicity resolves to \leq Grade 2. Resume at next lower dose unless already performed for the toxicity that led to the use of the growth factor. Growth factor use as per current treatment guidelines.

Hepatic Toxicities

Alanine aminotransferase (ALT) and aspartate aminotransferase (AST) elevation are considered as ADR with the use of abemaciclib. The following information in Table 3 must be included in investigator-sponsored protocols for hepatic monitoring:

Hepatic Toxicity Dose Management Guidelines	
Monitor ALT prior to the start of abemaciclib therapy, every 2 weeks for the first 2 months, monthly for the next 2 months, and as clinically indicated.	
CTCAE Grade for ALT and AST	Action

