Grade 1 ($>ULN-3.0 \times ULN$), Grade 2 ($>3.0-5.0 \times ULN$), WITHOUT increase in total bilirubin above $2 \times ULN$	No dose modification required
Persistent or Recurrent Grade 2, or Grade 3 ($>5.0-20.0 \times ULN$), WITHOUT increase in total bilirubin above $2 \times ULN$	Suspend dose until toxicity resolves to baseline or Grade 1. Resume at next lower dose.
Elevation in AST and/or ALT $>3 \times ULN$ WITH total bilirubin $>2 \times ULN$, in the absence of cholestasis	Discontinue abemaciclib
Grade 4 ($>20.0 \times ULN$)	Discontinue abemaciclib

Details for hepatic monitoring depend upon the severity and persistence of observed laboratory test abnormalities. If a study patient experiences elevated ALT $5 \times ULN$ and elevated TBL $2 \times ULN$, or ALT $8 \times ULN$, liver tests, including ALT, AST, TBL, direct bilirubin, gamma-glutamyl transferase (GGT), and creatine phosphokinase (CPK), should be repeated within 3 to 5 days to confirm the abnormality and to determine if it is increasing or decreasing. If the abnormality persists or worsens, clinical and laboratory monitoring should be initiated by the investigator, based on the hepatic monitoring tests below in Appendix B.

Diarrhea

At enrollment, patients should receive instructions on the prompt management of diarrhea. In the event of diarrhea, supportive care measures should be initiated as early as possible. These include the following:

CONFIDENTIAL

This material is the property of the [UC Irvine Chao Family Comprehensive Cancer Center](#). Do not disclose or use except as authorized in writing by the study sponsor.

- At the first sign of loose stools, the patient should initiate antidiarrheal therapy (e.g. loperamide) and notify the investigator for further instructions and appropriate follow up.
- Patients should also be encouraged to drink fluids (e.g., 8 to 10 glasses of clear liquids per day).
- Site personnel should assess response within 24 hours.
- Refer to table below for additional information for diarrhea management and dose modification.

Diarrhea Dose Management Guidelines	
At the first sign of loose stools, start treatment with antidiarrheal agents, such as loperamide.	
CTCAE Grade	Action
Grade 1	No dose modification required
Grade 2	If toxicity does not resolve within 24 hours to ≤ Grade 1, suspend dose until resolution. No dose reduction is required.

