Grade 2 that persists or recurs after resuming the same dose despite maximal supportive measures	Suspend dose until toxicity resolves to ≤Grade 1.
Grade 3 or 4 or requires hospitalization	Resume at next lower dose.

Dose level reductions should be made in 50 mg increments. For example, if the starting dose of abemaciclib for a study is 150 mg q12 hours, dose reduction 1 would be 100 mg q12 hours, dose reduction 2 would be 50 mg q12 hours.

General Guidance for Interstitial lung disease (ILD)/Pneumonitis events

Interstitial lung disease (ILD) / pneumonitis has been identified as an adverse drug reaction for abemaciclib. Adverse events reported included events such as interstitial lung disease, pneumonitis, obliterative bronchiolitis, organizing pneumonia, pulmonary fibrosis. The majority of events were Grade 1 or Grade 2 with serious cases and fatal events reported.

Monitor for clinical symptoms or radiological changes indicative of ILD/pneumonitis and please ask patients to report any new or worsening pulmonary symptoms. Symptoms may include hypoxia, cough, dyspnea, or interstitial infiltrates on radiologic exams.; these symptoms should be investigated and treated as per local clinical practice and/or guidelines (including corticosteroids as appropriate). Infectious, neoplastic, and other causes for such symptoms should be excluded by means of appropriate investigations. Investigations may include imaging such as high resolution computer tomography (HRCT), bronchoalveolar lavage (BAL), and biopsy as clinically indicated (see also Table).

Interstitial Lung Disease (ILD)/Pneumonitis

ILD/Pneumonitis Dose Management Guidelines	
CTCAE Grade	Action
Grade 1-2	No dose modification required
Grade 2 that persists or recurs after resuming the same dose despite maximal supportive measures within 7 days to baseline or Grade 1	Suspend dose until toxicity resolves to ≤Grade 1. Resume at next lower dose.
Grade 3-4	Discontinue abemaciclib

Non-hematological Toxicities (excluding Diarrhea, ALT Increased, and ILD Pneumonitis)

Non-Hematological Toxicity Dose Management Guidelines (excluding Diarrhea, ALT

CONFIDENTIAL

This material is the property of the [UC Irvine Chao Family Comprehensive Cancer Center](#). Do not disclose or use except as authorized in writing by the study sponsor.

Increased, and ILD Pneumonitis)	
Event	Action
Grade 1-2	No dose modification required

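### Read by CTCAE grade, the Section 4.2 rule for coinciding toxicities can outrank two discontinuation rows of the Section 4.2.1 tables

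*Combined protocol and SAP*

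**What the plan says.** Section 4.2 names CTCAE version 5.0 as the grading scale. The next sentence gives the only rule for toxicities in more than one organ system: "Dose adjustments should be made according to the system showing the greatest degree of toxicity". The word degree is not defined.

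Section 4.2.1 opens with "Please refer to the following tables for dose modifications for adverse reactions related to abemaciclib" and gives separate tables by organ system. The rows that matter here are:

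- **Hematologic.** A first Grade 3 event means a hold until Grade 2 or lower, and the cell adds "Dose reduction is not required". The row "Grade 3, recurrent, or Grade 4" means a hold, then resumption one level down.
- **Diarrhea.** The row "Grade 3 or 4 or requires hospitalization" leads to resumption one level down. Its action appears to share a cell with the row above, which holds the drug until Grade 1 or lower.
- **ILD/pneumonitis.** Grade 3-4 means abemaciclib is discontinued, with no hold and no route back.
- **Hepatic.** AST and/or ALT above 3×ULN together with total bilirubin above 2×ULN, without cholestasis, means discontinuation. So does Grade 4 AST/ALT (above 20×ULN).

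Sections 4.2.2, 4.5 and 5.6 add general discretion to stop treatment. None of them ranks the tables.

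**The concern.** A rule that lets the highest-graded organ system set the dose works only if severity of action rises with grade in the same way in every table. Here a Grade 3 lung event stops the drug, while a Grade 4 blood or bowel event does not. A patient with both could, on the natural reading of Section 4.2, be managed by the milder table and restarted.

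The pairing is clinically plausible. Section 4.2.1 reports Grade 3 and 4 neutropenia with abemaciclib, and serious and fatal ILD events. It also provides for corticosteroid treatment of ILD, so improvement below Grade 3 during a hold is foreseeable. At stake is rechallenge after an event for which the protocol's own table ends treatment. Compliance is also unclear, since Section 7.4 treats wrong dosage as a violation reportable within 5 business days, and two careful readers could classify the same restart differently.

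**Working it through.** No arithmetic applies. The check sets the rule beside the tables, taking degree as CTCAE grade and reapplying the rule as grades change.

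**Step 1: Grade 3 ILD with another event at its peak**

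| Coinciding event | System the rule selects | Action selected | ILD table | Result |
|---|---|---|---|---|
| Hematologic Grade 4 | Hematologic | Hold, resume one level down | Discontinue | Conflict |
| Diarrhea Grade 4 | Diarrhea | Hold, resume one level down | Discontinue | Conflict |
| AST/ALT Grade 4 | Hepatic | Discontinue | Discontinue | None |
| Any event at Grade 3 | Tie | Rule silent | Discontinue | Not outranked |
| Any event at Grade 2 or lower | ILD | Discontinue | Discontinue | None |

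Grade 4 ILD can be tied but never outranked by the graded rows above. The Grade 3-4 action cell for other non-hematologic toxicities is blank in the text as read, so I draw nothing from it.

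**Step 2: order of onset and recovery**

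- *Onset.* If ILD reaches Grade 3 while the other event is at Grade 2 or lower, ILD is the greatest degree and the rule has already selected discontinuation. The other event must therefore be at Grade 3 or higher at that moment, and at Grade 4 for some time alongside the Grade 3 ILD.
- *Recovery, ILD first.* If ILD falls below Grade 3 before the other event does, the rule never selects the ILD stop. It may pass through a Grade 3 tie, where it says nothing. Once the other event reaches its resumption threshold (Grade 2 or lower for hematologic, Grade 1 or lower for diarrhea), the selected table allows a restart.
- *Recovery, other event first.* If the other event falls below Grade 3 while ILD is still at Grade 3, ILD is the greatest degree and the rule itself selects discontinuation.
- *Dose level.* A patient already on 50 mg twice daily has no lower level, so both tables end in stopping.

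**Step 3: the combined hepatic row**

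Within the liver table, action does not follow transaminase grade alone. Without the bilirubin rise, "Persistent or Recurrent Grade 2, or Grade 3" means a hold and a lower dose; with it, AST/ALT above 3×ULN means a stop. The table puts above 3 to 5×ULN at Grade 2 and above 5 to 20×ULN at Grade 3. It gives no bilirubin grades, so I assume that the highest-graded liver finding sets the liver grade.

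- Liver at Grade 2: outranked by Grade 3 or 4 hematologic toxicity or diarrhea.
- Liver at Grade 3: outranked by Grade 4 hematologic toxicity or diarrhea.

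In each case the rule selects a resumption row and the hepatic table orders a stop. Timing matters in the same way. If the liver becomes the highest-graded system while its criteria still hold, the rule selects discontinuation.

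**Step 4: text that might settle it**

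- Section 4.2.1 sends the reader to all the tables without ranking them.
- The diarrhea guidance that follows Section 4.4.1 refers dosing on restart back to Section 4.2.1.
- Section 4.2.2 asks only that discontinuation be considered after 14 days without recovery.
- Sections 4.5 and 5.6 allow stopping for unacceptable or unsafe toxicity.

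None says that the strictest action prevails.

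**The case against.** The strongest reply is that the conflict needs three readings, each of which can be refused. Degree could mean clinical seriousness, in which case ILD would govern. Dose adjustment could exclude permanent discontinuation, leaving the stop rows outside the rule. And a general sentence need not switch off a specific, unconditional row when Section 4.2.1 points to every table. An investigator who simply follows the ILD table stops the drug, and Sections 4.5 and 5.6 support that choice.

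Much of this stands. A reader might infer that the protocol directs rechallenge after Grade 3 ILD; it does not. It leaves a reading open that permits it. That reading is still the natural one, because the CTCAE scale is named in the sentence just before the rule. The stop rows also sit in tables introduced as dose modifications, so they are not clearly outside it. Discretion reduces the risk without making the rule agree with its tables.

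A reader might also infer that the rule cancels a required reduction when a first Grade 3 hematologic event coincides with a persistent Grade 2 event elsewhere. The documents do not support this as a conflict. The hematologic cell says only "Dose reduction is not required", so reducing for the Grade 2 event complies with both tables.

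**Conclusion.** The point holds as a minor safety-wording error. With degree read as CTCAE grade, the Section 4.2 rule can select resumption where a Section 4.2.1 table orders discontinuation. This happens in two settings: Grade 3 ILD with Grade 4 hematologic toxicity or Grade 4 diarrhea, and the combined transaminase-bilirubin criterion with a higher-graded hematologic or diarrhea event.

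The conclusion assumes that degree means grade, that the rule covers discontinuation rows, and that onset and recovery fall in the order described. The documents give no co-occurrence rate and no ILD recovery time, so no patient frequency can be stated; the situation should be uncommon. A reader might infer a threat to the trial's results. There is none: pCR, the Simon two-stage boundaries and the error rates do not depend on this sentence.

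**What to change.** Replace the Section 4.2 sentence with: *When toxicities occur in more than one system, the most restrictive action required by any applicable table in 4.2.1 governs, and any discontinuation criterion overrides all other actions.*

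This takes one sentence in an amendment and needs no new data or procedures. The downside is an occasional extra dose reduction or discontinuation, each already ordered by an existing table.
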